# **ETC Rejection Protocol**

Borderline	Mini Pulse     No change in maintenance immunosuppression
ACR 1A	
 
Steroid Pulse
 
6 week prednisone taper
 
Rebiopsy in 1 month if SCr not improved
 

ACR 1B, 2A	
 
Thymoglobulin (7 days)
 
6 week prednisone taper
 
If on belatacept and Prograf, reduce Prograf goal trough to 3-5 ng/ml. Then taper per protocol.
 
For patients on belatacept and weaned from Prograf, no change in maintenance immunosuppression.
 

ACR 2B	
 
Thymoglobulin (10 days)
 
6 week prednisone taper
 
If on belatacept and Prograf, reduce Prograf goal trough to 3-5 ng/ml. Then taper per protocol.
 
For patients on belatacept and weaned from Prograf, no change in maintenance immunosuppression.
 

ACR 3	
 
Thymoglobulin (14 days)
 
6 week prednisone taper
 
If on belatacept and Prograf, reduce Prograf goal trough to 3-5 ng/ml. Then taper per protocol.
 
For patients on belatacept and weaned from Prograf, no change in maintenance immunosuppression.
 

AMR	Plasmapheresis/ IVIG

ACR – acute cellular rejection, AMR – antibody mediated rejection

#### The DSMB will:

- Protect the welfare of the patient.
- Monitor interim safety data.
- Identify safety issues and suggest solutions regarding study design and conduct.
- Review the study protocol and any protocol amendments
- Review the methods of data collection and safety monitoring making recommendations for additions or adjustments to ensure the timely delivery of such data.

- Review and approve the DSMB charter that defines the safety and related parameters to be reviewed by the DSMB, the frequency of DSMB monitoring reviews, methods for review, and establish criteria for making recommendations to the principal investigator.
- Conduct a futility analysis based at the time when approximately 30% of the study subjects complete the 6-month data collection.
- Based on the data reviewed at each meeting, the DSMB will advise one of the following actions to the principal investigator:
  - Continue the study according to the protocol and any related amendments.
  - Modify the study protocol. Modifications may include, but are not limited to: changes in inclusion/exclusion criteria, frequency of visits or safety monitoring, and alterations in study procedures.
  - Discontinue the study overall or end participation in particular subgroup.

## **Stopping Rules**

The study as a whole may be stopped by the Investigator and DSMB if there are reasons for which continuation of study is no longer justified, such as:

- Unacceptable delay of study completion,
- Low recruitment rate,
- A large number of study participants with premature termination,
- Changed benefit-risk ratio according to the efficacy and/or safety results from this or parallel studies

Study enrollment suspended pending expedited review by the DSMB when:

• 5 of 10 patients in treatment arm (every 2-Month Belatacept infusion) experience acute rejection

Study enrollment continuation with expedited review by the DSMB when:

• 3 of 5 patients in treatment arm (every 2-Month Belatacept infusion) experience acute rejection

In case of premature termination of the entire study, the PI will ensure that IRB/ appropriate Regulatory Authorities are notified within 15 days.

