Belatacept immunosuppressive therapy was implemented in the Emory Transplant Center (ETC) beginning in August of 2011. Current dosing protocol requires post-transplant kidney patients who are treated with belatacept to receive an infusion every 1 month, which presents logistical challenges due to the high cost of infusions, the limited capacity of the sites administering infusions, and inconvenience to patients. Definitive clinical evidence is lacking for equivalent treatment outcomes for patients who receive infusions at one month (q-1M) intervals versus every two month (q-2M) intervals. Data from five year (Vincenti F, Blancho G, Durrbach A et al. J Am Soc Nephrol 2010) and ten year (personal communication, [name]) follow up of the phase II clinical studies suggest that there are no significant differences in the patient outcomes for q-1Mversus q-2 Mdosing intervals. However, conclusions regarding differential

outcomes for the dosing interval regimens were limited by small sample size and deserve further investigation.

We hypothesize that immunologically low risk patients who are stable on belatacept therapy at least one year post transplant can be safely transitioned from an every 1 month to an every 2 months belatacept schedule, without a decrease in renal function or an increase in acute rejection. The Emory Transplant Center is uniquely qualified to perform this every two month study. We perform approximately 230 kidney transplants per year, utilizing belatacept as standard therapy in all eligible patients (Epstein Barr Virus (EBV) positive, etc). We have performed almost 500 kidney transplants on patients using belatacept as the primary immunosuppressant medication between August 2011 and the present (May 2015). Based on this clinical volume and high rate of belatacept use, we propose to screen approximately 18 patients per month and estimate enrolling an average of 12 patients per month into the study, specifically converting 6 patients per month from a q-1 month to a q-2 month schedule.

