# 4.4 Study stopping rules

**4.4.1** Study enrollment continuation with expedited review by the DSMB will occur for a threshold incidence of biopsy proven acute rejection of 10% on a rolling basis consistent with the following number of subjects with the event of rejection per enrolled patients (modified Simon's two-stage design strategy for 75-85% probability):

Number of subjects with Rejection (n)	Number of subjects enrolled in Q8 group
2	14
4	41
7	83

**4.4.2** Study enrollment suspension pending expedited review by the DSMB will occur for a threshold incidence of biopsy proven acute rejection of 20% on a rolling basis consistent with the following number of subjects with the event of rejection per enrolled patients (modified Simon's two-stage design strategy for 75-90% probability):

Number of subjects with Rejection (n)	Number of subjects enrolled in Q8 group
3	14
5	35
15	83

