# 6.8 Data Safety Monitoring Board (DSMB)

A Data Safety Monitoring Board will be established to monitor the safety of the patients during this trial. The initial meeting of the DSMB will occur prior to the start of the study in which study start will be defined as the date on which the first patient enrolled in the study. Subsequent meetings will occur three months from study start and then every six months thereafter. The DSMB will be composed of 3 official members who are members of the Transplant Nephrology, Transplant Surgery, or the Nephrology community. DSMB members must be independent of this study and may not serve as investigators or participate in the care of subjects enrolled in this study. See Appendix 2 for DSMB membership and Appendix 3 for DSMB charter.

DSMB recommendations to modify or prematurely terminate the study shall require a unanimous vote of all voting DSMB members.

To reduce the risk of disclosure of study information to non-DSMB members, board members shall not copy, disseminate, communicate, or allow access to information pertaining to this study. Any copies of materials prepared for distribution to DSMB members will be clearly labeled as confidential. All materials will be identified only with subjects' unique study identification number and personal information that could lead to the identification of the study subject will not be made available to the DSMB membership. All communications and confidential study data will be stored in a secured area by DSMB members.

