# 8. Study Population

The trial population consists of adults ≥18 years of age who are first-time transplant recipients of either living donor or deceased donor renal transplants. Patients of all races and ethnicities will be included.

This is an intention to treat, randomized, controlled trial. There will be a total of 166 subjects, randomized in equal numbers, 83 patients in each arm. We anticipate needing to consent/enroll 200 patients to achieve 166 randomized subjects accounting for an approximate 15% screen failure rate. All patients will be actively followed in the study for 12 months following enrollment. The study is projected to last 2 years.

Before any study procedures are performed, the details of the study will be described to subjects, and they will be given a written informed consent document to read. Patients who consent to participate in the study will sign and date the informed consent document in the presence of study personnel. Only patients who have given informed written consent will be included in this study.

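### Section 4.4 and the DSMB charter set two unreconciled lists of q-2M rejection triggers for the same two enrollment actions, and no available text says which governs

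*Combined protocol and SAP*

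**What the plan says.** Section 4.4 (Study stopping rules) has two tiers.

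- The milder tier, 4.4.1: "Study enrollment continuation with expedited review by the DSMB will occur for a threshold incidence of biopsy proven acute rejection of 10" percent, at 2/14, 4/41 or 7/83.
- The stricter tier, 4.4.2: "Study enrollment suspension pending expedited review by the DSMB will occur for a threshold incidence of biopsy proven acute rejection of 20" percent, at 3/14, 5/35 or 15/83.

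The denominator column is headed "Number of subjects enrolled in Q8 group", and the counts are said to apply on a rolling basis. The event is biopsy-proven acute rejection.

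The charter's Stopping Rules use the same two actions. Enrollment is suspended for expedited review when "5 of 10 patients in treatment arm (every 2-Month Belatacept infusion) experience acute rejection", and continues with expedited review when "3 of 5 patients in treatment arm (every 2-Month Belatacept infusion) experience acute rejection". The event there is acute rejection, without the biopsy qualifier.

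Section 6.8 makes the charter part of this protocol: "See Appendix 2 for DSMB membership and Appendix 3 for DSMB charter". Both lists are current text, and neither is in an amendment log. On arm size, Section 8 states: "There will be a total of 166 subjects, randomized in equal numbers, 83 patients in each arm".

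**The concern.** A stopping rule should tell the study team and the board, without discussion, whether the next patient may be enrolled. Here the study team could follow Section 4.4 while the board follows its charter, which by its own list of duties sets the criteria for the board's recommendations. The two could then disagree on whether enrollment is on hold. These rejection counts are the only numeric enrollment hold in the available text.

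The charter list also has faults of its own. Its milder action needs a higher rejection proportion than its stricter one. It has no count beyond 10 patients, and it does not say whether 5 and 10 mean the first patients enrolled or any such group.

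**Working it through.** **The triggers side by side (q-2M arm)**

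| Action | Section 4.4 | Charter |
|---|---|---|
| Continue with expedited review | 2/14 = 14.3%, 4/41 = 9.8%, 7/83 = 8.4% | 3/5 = 60% |
| Suspend pending review | 3/14 = 21.4%, 5/35 = 14.3%, 15/83 = 18.1% | 5/10 = 50% |

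Within the charter the order is reversed: 60% for the milder step, 50% for the stricter one.

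**Two readings of the 3/14 row**

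1. Rolling, so the count applies once reached. Three rejections among the first five patients meet the suspension count of 3. The charter names the same result as continuation with expedited review. The two texts clash directly.
2. Only at the 14th enrollment. Three rejections in 14, for example in patients 2, 8 and 14, suspend under 4.4.2. They are neither 3 of 5 nor 5 of 10, so no charter trigger is met.

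**How far apart the counts are**

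Patients are taken as independent, each counted by eventual outcome, with true rejection rate p. Then P(X ≥ r) = 1 − Σ C(n,k) p^k (1−p)^(n−k), summed over k = 0 to r−1.

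At p = 0.20:

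- 3 or more of 14: 1 − (0.0440 + 0.1539 + 0.2501) = 0.552
- 5 or more of the first 10: 0.033
- 3 or more of the first 5: 0.0512 + 0.0064 + 0.0003 = 0.058

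At p = 0.30 the three values are 0.839, 0.150 and 0.163.

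The cumulative chance of meeting 4.4.2 at p = 0.20 is 0.55 by 14 patients, 0.87 by 35 and 0.91 by 83. If the charter's 10 means any 10 consecutive patients, its suspension rule is met with probability 0.23 within the first 35 and 0.50 within 83, against 0.033 for the first 10.

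At the planned 1-2% rate (Section 10), 3 or more of 14 has probability 0.0003 to 0.0025, and 3 or more of the first 5 has 0.00001 to 0.00008. Section 4.4.2 as a whole is met 0.04% to 0.29% of the time, and 4.4.1 0.9% to 3.7%.

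**Why the time of counting must be stated**

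Section 1 plans on "specifically converting 6 patients per month from a q-1 month to a q-2 month schedule". At that pace the 14th q-2M patient enrolls 13/6 = 2.2 months after the first, so few 12-month outcomes are known by then. I simulated evenly spaced enrollment with a constant hazard giving 20% at 12 months; the hazard shape is an assumption.

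- Counts taken only at the 14th and 35th enrollments: 4.4.2 is met in about 3% of trials by the 35th. The charter's 5 of 10 is met by then in about 0.1% (first 10) or 0.2% (any 10).
- Counts for the first 14 and first 35 patients updated until enrollment ends: 4.4.2 is met in about 80%. The charter is met in about 3% (first 10) or 19% (any 10).

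**The case against.** The best defense is that the lists are complementary. The charter looks at 5 and 10 patients and Section 4.4 at 14, 35, 41 and 83. Neither says that its triggers are the only ones. If either is enough, patients 2, 8 and 14 is simply one rule firing while the other is silent. If the 3/14 row is read only at the 14th enrollment, 3 of 5 followed by suspension at 14 is a sequence and not a contradiction. This is a fair reading, and it rules out saying that the documents flatly give opposite orders for three rejections in five patients: that holds only on the rolling reading, and continuing there means continuing with expedited review. But no available text says that either trigger is enough, and the rolling wording favors the reading under which the two clash.

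On the event, Section 10 says rejection is collected on the final biopsy-proven result, so the missing qualifier in the charter is a minor point. The same sentence does, however, also mention clinically suspected rejection.

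Text just ahead of the charter's list of duties was not available for this review, so a statement of precedence there cannot be excluded.

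A reader might also take 0.91 against 0.03 as the chance of a missed suspension, or conclude that a rejection signal would go unseen. The documents support neither. The probabilities only show how often each rule is met. Either trigger brings expedited review, Section 10 has the board told of all serious adverse events, and the charter has ad hoc review done within 4 days of a request.

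**Conclusion.** The inconsistency stands and should be fixed. Two current lists give different q-2M counts for the same two actions, with no stated precedence. The gap is large in the range the rule is meant for: at a true 20% rejection rate, 0.55 for 3 or more of 14 against 0.03 for 5 or more of the first 10. It is of little practical weight if the planned 1-2% rate is right, but a stopping rule is written for the case where it is not.

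The figures assume independent patients and eventual outcomes. The charter comparison also depends on whether its 10 means the first 10 or any 10. That the lists differ rests on none of these assumptions. What is at stake is clarity about when enrollment is on hold. The probabilities that Section 4.4 attaches to its modified Simon design play no part in this conclusion.

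**What to change.** Replace the charter's 3-of-5 and 5-of-10 triggers with the 4.4.1 and 4.4.2 boundaries, worded identically in both places. Define the event as biopsy-proven acute rejection in the q-2M arm. State that each count applies as soon as it is reached among the first n q-2M patients, so that three rejections at or before the 14th patient suspend enrollment, and that the counts for those patients are updated while enrollment is open. Obtain DSMB sign-off.

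The counting rule has to be part of the change. If the charter's triggers were deleted and the counts fixed at the nth enrollment, there would be no numeric trigger before the 14th q-2M patient. With the rule above, two early rejections prompt review and three suspend, so nothing is lost by dropping 3 of 5.

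The cost is one wording amendment and one sign-off, with no added patients or data. False alarms stay rare: at 1-2% rejection, counting eventual outcomes, suspension is triggered in about 0.04% to 0.3% of trials and expedited review in 0.9% to 3.7%.

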### The Sponsor-Investigator

The principal investigator is responsible to the DSMB to:

- Provide regular updates to the DSMB regarding the trial progress, including any protocol
  amendments or issues that could potentially affect the safety of the subjects or the overall
  integrity of the study.
- Document and communicate the decisions to the remainder of the Study Team for

# Belatacept Q-1Month vs Q 2 Month Intervals

- implementation.
- Communicate all pertinent regulatory information to all Regulatory Authorities as appropriate.
- Securely archive all DSMB documentation following the completion of the study and termination of the DSMB activities.

# **DSMB** Procedures

# Scheduled meetings

- A full DSMB meeting will be held prior to the start of the study/first patient enrolled. After the initial meeting, safety review of data by the full DSMB will occur 3 months after the first patient is enrolled and then every 6 months thereafter.
- Further reviews may be requested by the DSMB Chair or the principal investigator at any time.
- Serious adverse events (including narratives) will also be provided for DSMB review.
- Ad hoc review will be done no later than 4 days following the request.
- DSMB meetings may be face-to-face or via telephone conference at the DSMB Chair's discretion.

### Quorum

A quorum of 2 voting DSMB members are required at scheduled meetings, phone conferences, and unscheduled meetings. A recommendation to continue the protocol without modification can be made by 2 voting DSMB members, however all 3 members must be present for any decisions to modify the protocol or prematurely stop the trial.

Page 19

### **Data Safety Monitoring Plan (DSMP)**

### **Belatacept Q2M Dosing study Monitoring Plan**

### Scheduling visits:

- The research coordinator will inform the independent monitor of the first patient enrollment so that study monitor can plan to hold the first monitor visit within 2 weeks.
- Monitor visits will be scheduled in advance with research coordinator.
- Monitor visit confirmation to be sent via email or fax at least 24 business hours ahead of visit, noting scheduled hours and which charts to be reviewed.
- Scheduled visits cancelled or revised by monitor will require monitor to notify [name] via email ([contact])
- Monitor is responsible for initiating all discussions on scheduling visits and for insuring that they are arranged in a timely manner and with an appropriate frequency.

# During visit:

- Monitor will complete sign in log located in E426 above fax machine. Incomplete sign in log may result in delay of Emory authorizing DocsGlobal timesheet.
- Monitor will discuss missing source data or repeating identical queries with coordinator. Items
  unable to be resolved quickly will be entered into monitoring letter. Items resolved will not be
  entered into monitoring letter.
- Monitor will set aside time at each visit to review queries with coordinator. Queries resolved during review with coordinator will not be entered into monitoring letter.
- Previously monitored visits completed by another monitor will not be re-monitored.
- Regulatory monitoring will occur in conjunction with our regulatory coordinator, [name].
- Investigational Drug Services monitoring visits will be scheduled by the monitor via Emory University's Investigational Drug Services online calendar at www.ocr.emory.edu/ids

## **Reports and Communication**

[figure not shown]
- Monitor reports are to be as succinct as possible.
- Monitor and coordinators will respond to email communications within 48-72 hours.
- All communication will be in email or written hard copy. Any communication in hard copy form will be received by this site within 48-72 business hours.

# **Supervisory Details**

- The monitor will bring his/her own laptop to the site in order to review medical records.
- It is expected that the monitor already has tools in place which can be generalized to this study.
- It is expected that the monitor will review the protocol prior to starting. Up to one hour of prep time will be reimbursed by site.

Version 5.0 Version Date: 10JUL2018 Page 20

# Appendix5

**Schedule of Events**
